6.5 CONCOMITANT THERAPY

All concomitant medications will be recorded each time a subject comes to clinic. Hydroxyurea is permitted as a concomitant medication but hydroxyurea dose change during the study is not permitted.

Participants will be asked always to check with the PI or clinical study staff before taking a new medication. Medications that are Inducers or inhibitors of cytochrome CYP3A4 may affect voxelotor metabolism, and participants will be told to avoid these medications.

6.5.1 RESCUE MEDICINE

Not-applicable

7 STUDY INTERVENTION DISCONTINUATION AND PARTICIPANT DISCONTINUATION/WITHDRAWAL

7.1 DISCONTINUATION OF STUDY INTERVENTION

If a participant discontinues voxelotor before completing the 2nd CPET but is willing to resume treatment on study, then the participant must take voxelotor continuously for at least 1 month before performing the 2nd CPET. If the participant discontinues voxelotor and is unwilling to resume treatment per the study protocol, then the participant will be discontinued from the study. Only routine clinical laboratory monitoring blood work results will be collected at the time of treatment discontinuation, not study labs.

7.2 PARTICIPANT DISCONTINUATION/WITHDRAWAL FROM THE STUDY

Participants are free to withdraw from participation in the study at any time upon request.

An investigator may discontinue or withdraw a participant from the study for the following reasons:

- Pregnancy
- Significant study intervention non-compliance
- If any clinical adverse event (AE), such as hypersensitivity to the study drug, laboratory abnormality, or other medical condition or situation occurs such that continued participation in the study would not be in the best interest of the participant
- If the participant meets an exclusion criterion (either newly developed or not previously recognized) that precludes further study participation
- Participant unable to perform CPET
- Participant unexpectedly moves to another location not within travel distance of the exercise lab and is unable to complete the 2nd CPET before moving

The reason for participant discontinuation or withdrawal from the study will be recorded on the Case Report Form (CRF). Subjects who sign the informed consent form and subsequently withdraw, or are withdrawn or discontinued from the study, will be replaced.

7.3 LOST TO FOLLOW-UP

A participant will be considered lost to follow-up if he or she fails to return for both of the study visits before study drug initiation and both of the study visits after initiation of study drug, or if he or she fails to show for scheduled CPETs and is unable to be contacted by the study site staff.

The following actions must be taken if a participant fails to return to the clinic for a required study visit:

- The site will attempt to contact the participant and reschedule the missed visit within 1-2 weeks and counsel the participant on the importance of maintaining the assigned visit schedule and ascertain if the participant wishes to and/or should continue in the study.
- Before a participant is deemed lost to follow-up, the investigator or designee will make every effort to regain contact with the participant, including at least 3 telephone calls using all available phone numbers for the patient and the emergency contact, 3 emails, letters to the participant and to the participant's pediatrician or PCP. These contact attempts will be documented in the participant's medical record or study file.
- Should the participant continue to be unreachable, he or she will be considered to have withdrawn from the study with a primary reason of lost to follow-up.

8 STUDY ASSESSMENTS AND PROCEDURES

8.1 EFFICACY ASSESSMENTS

Efficacy of study drug will be assessed as follows:

- CPET (cardiopulmonary exercise test) is non-invasive and will be performed using a motorized treadmill (Trackmaster Model TMX428, Full Vision, Inc.). Participants will have their nose clipped and breathe through a mouthpiece with a nonbreathing valve. Breath by breath gas exchange data will be collected and analyzed using a VMax Encore 29C metabolic cart (CareFusion Corp, San Diego, CA). The participants will have EKG leads and pulse oximetry monitoring while running on a treadmill that increases in incline incrementally to induce peak physical effort according to a modified Bruce protocol based on patient age, size, and exercise ability. A peak exercise response will be defined as a respiratory exchange ratio of greater than 1.1 or to patient's volitional fatigue. The patient exercises for 8-12 minutes. Approximately 1.5 hour will be allotted for the entire CPET visit, which will include checking in, explanation of the procedure, preparation and setup for the test, the exercise test itself, and post-test debriefing. This exercise test will be done twice by each participant: once before and once after starting the study drug. The CPET report will be provided to the participant.
- During exercise the following will be measured and recorded:
 - · 12-Lead ECG
 - · Pulse oximetry
 - · Blood Pressure
 - · Peak HR
 - · Peak VO₂ (ml/kg/min)

- · Peak VO₂ (L/min)
 - · Respiratory Exchange Ratio (RER)
 - · O₂ Pulse
 - · VE/VO₂
 - · VE/VCO₂
 - · VO₂/HR
 - · VAT (ventilatory anaerobic threshold)
 - · Percent VO₂ at VAT
- Blood will be drawn for study labs once before the study drug and once after. Study labs will be performed by the research laboratory of [name] at UCSF. Blood samples will be sent by FEDEX overnight.
 - Blood work as part of regular standard of care will continue to be done during the study.
 - The “Patient Global Impression of Change” and the “Clinician Global Impression of Change” single-question surveys will be completed by the participant and the clinician, respectively, at the final study visit.

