Cardiopulmonary exercise testing, or CPET, is the commonly accepted benchmark of aerobic capacity^{10, 11}. While a subject is performing a standardized exercise protocol with incremental ramping, either on a bicycle or a treadmill, and breathing through a non-rebreathing mouthpiece, expired air is analyzed via breath-by-breath sampling. Fractions of oxygen, carbon dioxide, air volume and flow are measured to calculate oxygen uptake (VO₂), carbon dioxide output (VCO₂) and minute ventilation, all in real-time. The peak VO₂ (VO₂ max) is the maximal ability of the subject to take in and utilize oxygen, which is the functional aerobic exercise capacity. Peak VO₂ is determined by the cardiovascular, pulmonary, musculoskeletal, as well as the hematologic system. CPET is most commonly done in adults, but is also utilized in children, particularly in those with cystic fibrosis and congenital heart disease, as well as in adolescents with sickle cell disease¹².

What is known about exercise testing in SCA?

Although reports are limited, exercise in SCA has been investigated, and the field is growing. Experience in these investigations, including GBT's phase 1/2 voxelotor study, has reassured that maximal exercise testing is safe in SCA and does not induce pain or other sickle cell crisis^{1, 8, 13, 14, 24}. Studies have shown that children and adults with SCA exhibit decreased cardiopulmonary fitness, most informatively demonstrated through cardiopulmonary exercise testing (CPET) and peak oxygen consumption. Peak VO₂ in adolescents and adults with SCA in ergometric bicycle CPET was as much as 30% lower than controls, even after adjusting for BMI and hemoglobin^{15, 16, 17}. A study of more than 200 adults with SCA using a standard Balke treadmill exercise test found lower exercise capacity among participants than the general African American population, with lower exercise capacity associating with lower hemoglobin^{14, 18}. SCA is a systemic disease affecting all organs, and decreased peak VO₂ is likely multi-factorial. Anemia directly affects oxygen-carrying capacity, and low hemoglobin would be expected to compromise aerobic activity. Indeed, CPET before and after transfusion both in patients with chronic anemia conditions and in pre-surgical patients with anemia showed ~10% difference in

peak VO₂^{19,20}. Thus, low hemoglobin in SCA is likely one factor contributing to decreased exercise capacity, and increasing hemoglobin in SCA might improve VO₂ max.

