9.2 SAMPLE SIZE DETERMINATION

This is a pilot study of 10 patients to define the magnitude of change. Power cannot be calculated at this time.

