9.3 POPULATIONS FOR ANALYSES

There will be one dataset for this pilot study of 10 patients.

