9.4 STATISTICAL ANALYSES

9.4.1 GENERAL APPROACH

Peak VO₂ is measured as ml/kg/min or L/min and statistics will be presented as percent change between the peak VO₂ on voxelotor and baseline peak VO₂. As the primary objective of this study is to obtain clinical and laboratory information to justify a larger clinical efficacy trial of voxelotor in SCA patients, the results of this study will first be analyzed descriptively.

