9.4.2 ANALYSIS OF THE PRIMARY EFFICACY ENDPOINT(S)

The primary endpoint is peak VO₂, which is a quantitative measurement from the CPET instrument. There will be a single measurement as a baseline and another single measurement after the study drug for each participant. Paired t-test will be used to compare the 2 peak VO₂s.

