9.4.8 TABULATION OF INDIVIDUAL PARTICIPANT DATA

Individual participant data will be listed by measure and time point.

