9.4.9 EXPLORATORY ANALYSES

There are no exploratory analyses.

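### Does accepting volitional fatigue as a peak response leave the peak VO₂ comparison open to unmeasured changes in effort?

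*Protocol*

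**What the plan says.** Section 8.1 defines the end of a valid test: "A peak exercise response will be defined as a respiratory exchange ratio of greater than 1.1 or to patient's volitional fatigue". The two conditions are alternatives. Section 2.3.1 agrees, since testing stops when the participant reports fatigue or discomfort. Section 2.2 says of peak VO₂ that it "is the maximal ability of the subject to take in and utilize oxygen, which is the functional aerobic exercise capacity".

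The cardiopulmonary exercise test (CPET) is done once before and once on voxelotor. Section 8.1 lists RER, peak heart rate and the ventilatory anaerobic threshold (VAT), among others, as recorded during exercise, under the heading of efficacy assessments.

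On the analysis, section 9.4.2 says: "There will be a single measurement as a baseline and another single measurement after the study drug for each participant". The two values are compared by a paired t-test. Section 9.4.1 adds that "statistics will be presented as percent change between the peak" VO₂ values, and that results are first analysed descriptively. On size, section 9.2 says: "This is a pilot study of 10 patients to define the magnitude of change". Section 9.3 says: "There will be one dataset for this pilot study of 10 patients". Section 9.4.7 marks subgroup analyses as not applicable. Section 9.4.8 says: "Individual participant data will be listed by measure and time point". Section 9.4.9 says: "There are no exploratory analyses".

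**The concern.** Section 2.2 reads peak VO₂ as a maximal capacity, while section 8.1 accepts a test with no objective sign that the maximum was reached. Pairing removes differences between participants. It does not remove a change in effort within one participant between two single tests. There is no control arm, no blinding and no replicate test, and the hypothesis in section 9.1 is directional. If participants pushed harder at the second test, the stated analysis would count the gain as a change in peak VO₂.

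At stake would be the magnitude of change that this pilot is meant to supply to a larger trial. Sections 9.3, 9.4.7 and 9.4.9, read together, also seem to leave no place for an analysis that looks at effort.

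**Working it through.** **1. Is there a figure to reproduce?** No. Section 9.2 sets 10 participants and says that power cannot be calculated. The protocol gives no target effect, no standard deviation (SD) and no rate of submaximal tests. Everything in steps 2 and 3 is therefore an illustration under assumptions.

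**2. How far could unequal effort move the estimate?** Assume no drug effect. Let kB participants be short of their true peak by a fraction d at baseline only, and kF others at follow-up only. A short baseline reads 1 − d of the true value, so that participant's percent change is 1/(1 − d) − 1. A short follow-up gives −d. Hence

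shift in mean percent change = 100 × [(kB/10) × (1/(1 − d) − 1) − (kF/10) × d].

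| Participants short | d = 5% | d = 10% | d = 15% |
|---|---|---|---|
| 1 at baseline only | +0.53 | +1.11 | +1.76 |
| 1 at follow-up only | −0.50 | −1.00 | −1.50 |
| 3 at baseline only | +1.58 | +3.33 | +5.29 |
| 3 at follow-up only | −1.50 | −3.00 | −4.50 |
| 1 at each test, different people | +0.03 | +0.11 | +0.26 |
| Same person, same shortfall at both | 0 | 0 | 0 |

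For example, three at baseline with d = 15%: 100 × 0.3 × (1/0.85 − 1) = 5.29.

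The sign depends on which test falls short, and shortfalls at both tests nearly cancel. For scale, the 95% confidence interval half-width with 10 pairs is 2.262 × SD/√10. That is 4.29 points at an assumed SD of 6%, 7.15 at 10% and 10.73 at 15%. Of the tabulated shifts, only the two largest (+5.29 and −4.50) exceed the half-width at an SD of 6%. None exceeds it at 10% or 15%.

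**3. Would a different primary analysis be better?** There are three candidates.

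- *Adjusting for RER or peak heart rate.* The second values are measured on drug and may respond to it, so adjustment could remove part of the effect being estimated.
- *Keeping only pairs with RER above 1.1 at both tests.* This selects on a variable measured after treatment and shrinks a sample of 10. If three pairs dropped out, the half-width at an SD of 10% would rise from 7.15 to 2.447 × 10/√7 = 9.25. It would still not prove equal effort.
- *Leaving the all-pairs comparison as it is and showing the effort measures beside it.* This does not change the primary estimate.

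Only the third is free of an obvious cost, and it concerns presentation.

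**4. Does section 9 rule that presentation out?** No. Showing RER and heart rate next to VO₂ needs no second dataset and is not a subgroup analysis. Section 9.4.9 cannot be read as a bar on everything beyond the t-test either, because the synopsis and section 3 name an exploratory objective and endpoint (the global impression scales). Sections 8.1, 9.4.1 and 9.4.8 together provide for recording the measures, describing results first and listing individual data. In 10 participants, each person's RER and heart rate at both tests can be read from those listings.

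**The case for a change.** The strongest case for the concern is that the protocol is not merely silent. It fixes the either/or definition and then gives the effort measures no stated role in an uncontrolled, unblinded before-and-after comparison. A shift across the whole cohort would matter more than a few short tests. If mean effort rose by 3% with no drug effect, a two-sided 5% paired t-test would show a significant increase in 29.3%, 18.5%, 13.4% or 8.2% of such studies at an SD of 6, 8, 10 or 15%, against a nominal 2.5%. Stating the effort summary in advance would also prevent effort measures from being chosen after the results are seen, and would cost two or three sentences.

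What stands is that effort and drug effect cannot be fully separated in this design, and that an effort summary is useful to a reader. What does not stand is the step from there to a fault in the plan:

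- The 3% shift and the SDs are assumed. The protocol supports neither a size nor a direction.
- It works against unequal effort through an incremental test meant to bring out peak effort, preparation by an exercise physiologist, no expected peak VO₂ communicated to patients, and a certified laboratory.
- No stated decision depends on significance. The pilot is unpowered and first analysed descriptively.
- Supportive summaries of recorded CPET variables are what a protocol commonly leaves to the statistical analysis plan, which is not at hand here.

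A related worry, that the second test might follow a different treadmill protocol, adds little. Section 8.1 names one treadmill and one metabolic cart and says that this test is done twice.

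**Conclusion.** The concern does not hold. The reading of section 8.1 is right: fatigue alone suffices. But that is an accepted end to a peak exercise test, and the sections cited do not contradict one another. No direction or size of bias can be drawn from the protocol. The illustrations run from −4.5 to +5.3 points and depend entirely on assumed shortfalls, in up to three of 10 participants, at one test only. Neither test termination nor the all-pairs paired comparison would need to change, so the primary result would be the same. What remains is a preference about how measures that are already recorded and listed should be summarised. This conclusion assumes that the listings in section 9.4.8 cover the CPET measures named in section 8.1, as their wording indicates.

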8.2 SAFETY AND OTHER ASSESSMENTS

Screening and enrollment can occur in the same visit. Screening consists of physical exam and vital signs to ensure general good health of the patient, as well as reviewing labs and medication dose to ensure that the hemoglobin and Hydroxyurea dose have been stable for 3 months. The study procedure CPET will be explained to potential participants in detail at the screening/enrollment visit.

All visits will include physical examination, vital sign, standard of care labs, and assessment of adverse events, which will be entered into CRFs.

8.3 ADVERSE EVENTS AND SERIOUS ADVERSE EVENTS

8.3.1 DEFINITION OF ADVERSE EVENTS (AE)

Adverse event means any untoward medical occurrence associated with the use of voxelotor or performance of exercise testing, whether or not considered intervention-related (21 CFR 312.32 (a)).

8.3.2 DEFINITION OF SERIOUS ADVERSE EVENTS (SAE)

An AE or suspected AE is considered “serious” if it results in any of the following outcomes: death, a life-threatening adverse event, inpatient hospitalization, a persistent or significant incapacity or substantial disruption of the ability to conduct normal life functions, or any event that may jeopardize the

participant or require medical or surgical intervention. An AE for this study may be a hypersensitivity reaction in the form of bronchospasm requiring intensive treatment in the emergency room or clinic or result in hospitalization.

8.3.3 CLASSIFICATION OF AN ADVERSE EVENT.

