2.3 RISK/BENEFIT ASSESSMENT

2.3.1 KNOWN POTENTIAL RISKS

Physical risk

Voxelotor: The most common adverse reactions reported with incidence > 10% are headache, diarrhea, abdominal pain, nausea, fatigue, rash, and pyrexia. No significant toxicities requiring medical intervention have been reported. If a subject complains of intolerable side effects, voxelotor will be stopped and the subject will come off study. Voxelotor binds to hemoglobin. When the drug is stopped, voxelotor-modified hemoglobin will degrade, and no long-term risk is expected.

CPET: Aggravation of SCA symptoms during exercise testing is unlikely, because exercise testing is stopped when participants complain of fatigue or discomfort. Studies of exercise testing in patients with sickle cell disease have been published, including GBT's phase 1/2 voxelotor study, and no adverse events, such as pain crisis, have been reported.^{8, 13, 14-17, 24}

Venipuncture: The risks of drawing blood from a vein include fainting, local pain, bruising, swelling, or rarely an infection at the needle site. Patients routinely have blood draws as part of regular sickle cell care, and this study will take blood from the same venipuncture as routine care blood draws, no extra venipunctures are required. In the event of adverse effects to the subjects, necessary medical or professional intervention will be instituted immediately. Approximately 5 cc (1 teaspoon) of blood will be drawn for study labs on 2 occasions in the study.

Psychological risk

Voxelotor treatment: Most patients are already taking the medication for sickle cell disease. Adding another oral medication to be taken at the same time as the existing medication is unlikely to induce an adverse psychological effect.

CPET: Patients may experience potential anxiety, stress, and uncomfortable emotions if CPET results are not as they expected. As we do not know what the expected peak VO₂ will be for our patient population, we have no expected results for peak VO₂ and will not be communicating any expectations to our patients that might be anxiety-provoking. CPET will be explained to patients and patients will be prepared for CPET by the exercise physiologist to reduce apprehension and anxiety. A pediatric psychologist is part of the sickle cell care team and is available to provide counseling, if needed.

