8.3.3.1 SEVERITY OF EVENT

For adverse events (AEs), guidelines will be used to describe severity.

- **Mild** – Events require minimal or no treatment and do not interfere with the participant’s daily activities.
- **Moderate** – Events result in a low level of inconvenience or concern with the therapeutic measures. Moderate events may cause some interference with functioning.
- **Severe** – Events interrupt a participant’s usual daily activity and may require systemic drug therapy or other treatment.
-

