8.3.5 ADVERSE EVENT REPORTING

AEs will be reported to the GBT Medical Affairs Research Program at regular intervals as required by GBT. SAEs will be reported to GBT Pharmacovigilance or Designee and to the IRB within 24 hours after the investigator learns of the event. GBT or Sponsor-Investigator will be responsible for notifying the FDA of any unexpected fatal or life-threatening suspected SAE as soon as possible, but in no case later than 7 calendar days after GBT's initial receipt of the information.

Expected AEs will be recorded in CRFs.

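### The last limb of the SAE definition in section 8.3.2 is unqualified, so read literally a treated, expected reaction can become a 24-hour SAE

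*Protocol*

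**What the plan says.** Protocol section 8.3.2 calls an event serious if it leads to death, a threat to life, admission to hospital, or lasting or significant incapacity. It closes with a catch-all: "or any event that may jeopardize the" "participant or require medical or surgical intervention" (one sentence, split by a page break). The example that follows is a hypersensitivity reaction with "bronchospasm requiring intensive treatment in the emergency room or clinic or result in hospitalization", introduced as an AE rather than an SAE.

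Seriousness then decides how an event is handled:
- Section 8.3.5: "SAEs will be reported to GBT Pharmacovigilance or Designee and to the IRB within 24 hours after the investigator learns of the event". The same section says "Expected AEs will be recorded in CRFs" and sends AEs to GBT at regular intervals.
- Section 8.3.6: the duty to report SAEs applies whether or not the event is related to treatment, and also to events the protocol already lists.
- Section 8.3.4: events are captured until 7 days after the last day of participation if non-serious, and until 30 days after if serious.
- Section 8.4.2: an unanticipated problem that is an SAE is due within 24 hours, any other within 10 days.

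Section 8.3.3.3 names seven expected AEs: headache, diarrhea, abdominal pain, nausea, fatigue, rash and pyrexia.

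**The concern.** A seriousness definition has to separate events that need urgent reporting from those that do not. Here the second half of the closing limb sets no threshold. It does not say what kind of intervention counts, or what the intervention must be meant to prevent. The verb is also permissive, so a possible need for intervention is enough. Nothing in the protocol defines medical intervention.

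An investigator must therefore either follow the words, and send treated minor reactions down the SAE route, or apply a narrower meaning that the text does not state. Two people could classify the same event differently and both believe they complied. The trial has no DSMB (section 10.1.6) and relies on monitoring by the PI and IRB (section 10.1.7), so the rapid reports to the IRB are a main safety channel. They should carry a clear meaning.

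**Working it through.** The protocol gives no SAE rate or other figure on this point, so there is nothing to reproduce. The check is mainly textual.

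**Step 1: is intervention sufficient alone?** The two halves of the closing limb, jeopardy to the participant and need for intervention, are joined by a disjunction. Meeting either one is enough. Neither refers back to the outcomes listed before it.

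**Step 2: does the surrounding text limit it?** Two places hint at a narrower intent. The bronchospasm example in 8.3.2 concerns intensive emergency treatment or admission. Section 2.3.1, after listing common reactions, says "No significant toxicities requiring medical intervention have been reported". The example only illustrates, and it is labelled an AE. The sentence in 2.3.1 describes past experience and defines no term. Neither restricts the criterion.

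**Step 3: can the severity grade do the separating?** No, because every grade allows for treatment. The lowest grade reads "Events require minimal or no treatment and do not interfere with the participant’s daily activities". The wording for the middle grade refers to therapeutic measures, and that for the highest grade to a possible need for systemic drugs or other treatment. So even a mild event with minimal treatment could meet the literal wording of 8.3.2.

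**Step 4: follow one event through.** Take a reaction on the expected list that is treated with medication. This is an illustration, not a case in the protocol, and it assumes that medication counts as medical intervention.

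| Section | Handled as an expected, non-serious AE | Handled under the literal 8.3.2 |
|---|---|---|
| 8.3.5, 8.3.6 | CRF entry; AEs to GBT at intervals | GBT Pharmacovigilance and IRB within 24 hours |
| 8.3.4 | capture to 7 days | capture to 30 days |

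Being expected does not exempt the event, because 8.3.6 includes listed events.

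**Step 5: can the size be stated?** Inputs: seven reactions, each with incidence above 10% (section 2.3.1); 10 participants (section 9.2); treated share q, which the documents do not give. Taking 10% as a floor for each reaction and counting each reaction once per participant:

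Expected participant-events = 10 × 7 × 0.10 = 7.0

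Expected events meeting the literal wording = 7.0 × q

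| q (assumed) | Events |
|---|---|
| 0.10 | 0.70 |
| 0.25 | 1.75 |
| 0.50 | 3.50 |
| 0.75 | 5.25 |
| 1.00 | 7.00 |

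The result depends almost wholly on q. The 10% is also only a floor, and the protocol gives no exposure period for it. The table shows why no size can be claimed; it is not an estimate.

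**The case against.** The strongest reply is that context supplies the missing limit. The limb ends a list of grave outcomes, shares a clause with jeopardy to the participant, and is followed by an example of intensive treatment. Section 2.3.1 can report common headache and fever and still say that no significant toxicity needed medical intervention, which suggests the authors did not count routine symptom relief. Any error would also be towards over-reporting. This stands as evidence of intent, and many investigators may well apply the narrower sense. It does not change what the criterion says, and guessed intent is a poor basis for consistent classification.

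Four stronger readings might be inferred, and the documents support none of them:
- *That 8.3.2 contradicts the severity scale.* Severity grades intensity and seriousness concerns outcome. Section 8.3.3.1 never says that a treated event is non-serious.
- *That expected AEs go to CRFs and nowhere else.* Section 8.3.5 does not say so, and 8.3.6 foresees events that are both listed and serious. The distinction between the two routes is blurred; the reporting rules are not in flat conflict.
- *That a treated expected reaction becomes unexpected.* Section 8.3.3.3 names these reactions as expected, and the remark in 2.3.1 about significant toxicities sets no ceiling that ordinary treatment would breach.
- *That a reported SAE total will be inflated.* Section 9.4.4 lists severity, relationship, expectedness, dates, outcome and duration. It specifies no SAE count.

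**Conclusion.** The point holds as a defect in a stated rule. As written, needing intervention is enough to make an event serious, so the definition cannot tell a serious event from an ordinary treated one. The consequences that follow from the text are a 24-hour report to GBT Pharmacovigilance and the IRB, the 30-day capture window, and a real chance of over-classification or inconsistent classification. That a treated expected reaction is caught rests on one assumption: that medical intervention includes ordinary medication, which the protocol neither says nor excludes.

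How many events would be affected cannot be established from the documents. Inflation of SAE numbers is a risk, not a demonstrated result. The sample size, the primary endpoint and the efficacy analysis are untouched. The correction is worth making because it is cheap and sharpens safety reporting.

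**What to change.** In section 8.3.2:
1. Limit the closing limb to important medical events that may jeopardize the participant or require intervention to prevent one of the outcomes already listed in that section.
2. Add that treatment alone does not make an event serious.
3. Label the bronchospasm example an SAE.

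The severity scale in 8.3.3.1 and the reporting routes in 8.3.5 and 8.3.6 need no change for this point. The cost is about one sentence, the relabelled example and matching guidance on the AE form. The small downside is that the investigator must judge, event by event, whether an intervention was needed to prevent a serious outcome.
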